9.4.1 Adverse Event Reporting Period

After signing of the Informed Consent all significant medical conditions including signs/symptoms of the underlying disease and known pre-existing medical conditions found during the screening period and up to initiation of dosing will be captured as medical history. Any event/condition, including those related to participation in the study or study procedures, those not related to underlying disease or pre-existing medical conditions already part of medical

history, and occurring before first dose of study treatment will be captured as a non-treatment emergent AE.

Any event/condition noted once the subject receives their dose of study drug will be captured as a treatment emergent AE. All AEs and SAEs regardless of attribution will be collected until at least 90 days following the last administration of study drug or the subject's EOS visit, whichever is later. At the last scheduled visit, the Investigator should instruct each subject to report to the Investigator any subsequent AEs/SAEs that the subject's personal physician believes could be related to prior study treatment.

SAEs unrelated to study treatment and non-serious AEs are to be followed until the last scheduled study visit (EOS visit), with the outcome at that point of time to be recorded in the eCRF. SAEs related to study treatment (Serious Adverse Drug Reactions) are to be followed until resolution or until they return to baseline, stabilize, or the subject is lost to follow-up. Resolution of AEs and SAEs (with dates) should be documented on the AE eCRF and SAE form (if applicable) and in the subject's medical record to facilitate source data verification. For some SAEs, the Sponsor or its designee may follow up by telephone, facsimile, electronic mail, and/or a monitoring visit to obtain additional case details deemed necessary to appropriately evaluate the SAE report (e.g., hospital discharge summary, consultant report, or autopsy report).

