10.9 Safety Analyses

10.9.1 Treatment Emergent Adverse Events

A treatment-emergent AE (TEAE) is defined as an event that was not present prior to administration of the first dose of study treatment and present after the first administration or if it represents the exacerbation of an event that was present prior to the first administration.

Adverse events noted during the study will be coded to system organ classes (SOCs) and preferred terms (PTs) using the Medical Dictionary for Regulatory Activities (MedDRA) dictionary. The overall incidence of TEAEs will be summarized by treatment group and classified by SOC and PT. Deaths, AE severity, serious AEs, relationship to study treatment and study discontinuation due to AE will also be tabulated by treatment group. An AE will be considered related to study treatment if the Investigator indicated the event is at least “possibly” related or if the relationship is missing. Adverse events with missing start dates, but with stop dates overlapping into the treatment period will be counted as treatment emergent. All AEs will be listed in subject listings and summarized by numbers and percentages of subjects by treatment group.

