### **3.4. Unmasking**

#### **4. POPULATIONS DEFINITIONS**

The following analysis sets will be evaluated and used for presentation and analysis of the data.

Analysis sets defined by eye will be respect to each eye. For example, the Safety Analysis Set for the CE will be determined by measurements taken on the CE. The subject-level analysis sets consist of subjects who meet the criteria in at least one of the eye-level analysis sets.

**Screening Analysis Set:** Includes all subjects who signed the informed consent form.

**Safety Analysis Set (SAF):** All screened subjects who were randomized and received at least one dose of study treatment.

The disposition data will be presented for all screened subjects. The SAF will be the primary set for the analysis of the safety parameters. The SAF will also be used for descriptive summaries of demographics, baseline characteristics, and ocular/non-ocular medical history.

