## **5.6. Safety – Adverse events**

A treatment-emergent AE (TEAE) is defined as an event that was not present prior to administration of the dose of study drug (ultevursen or sham-procedure) and present after the dose or if it represents the exacerbation of an event that was present prior to the dose.

Adverse events will be summarized by treatment group separately as follows:

- For non-ocular AE:
  - by subject, therefore, in any tabulation, a subject contributes only once to the count for a given adverse event (System Organ Class [SOC] or Preferred Term [PT])
  - and during the overall study period (i.e., up to the last visit for the last subject).

- Time to onset will be calculated in hours, relative to the last dose received, irrespective of which eye received the last dose (i.e., TE or CE).
- For ocular AE:
  - by eye frequencies, separately for the TE and the CE, therefore, in any tabulation, an eye contributes only once to the count for a given AE (by SOC or PT). AEs that are reported in both eyes (i.e., OU) will be reported individually by eye in the tabular summaries.
  - and during the overall study period (i.e., up to the last visit for the last subject).
  - Time to onset will be calculated in hours, relative to the last dose received in the eye experiencing the ocular AE.

Unless otherwise stated, any summary of any type of TEAEs which includes the SOC and PT of the events will order the SOC and the PTs within the SOC by descending incidence of PT.

The following summary tables will be produced separately according to the type of AEs (ocular/non-ocular where applicable) as defined above:

- Overview of Ocular Adverse Events for Treatment Eye during the overall study period (Safety Population)
- Overview of Ocular Adverse Events for Contralateral Eye during the overall study period (Safety Population)
- Overview of Non-Ocular Adverse Events during the overall study period (Safety Population)
- Summary of Ocular Treatment-Emergent Adverse Events for Treatment Eye during the overall study period by MedDRA System Organ Class and Preferred Term (Safety Population)
- Summary of Ocular Treatment-Emergent Adverse Events for Contralateral Eye during the overall study period by MedDRA System Organ Class and Preferred Term (Safety Population).
- SAEs
- AESIs

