#### **5.6.1. Partial and Missing Date/Time for Adverse Events**

Imputation of missing/partial AE date/time will be done only to identify TEAEs.

AE onset dates

- Partially missing onset date/time will be imputed as follows:
  - When only Day is missing:
    - If Month & Year of the onset date are the same as Month & Year of the first administration date, the imputed onset date will be imputed as the minimum of the first administration date/time and the AE resolution date (imputed if needed).
    - Otherwise, the missing day will be replaced by “1.”
  - When Day & Month are missing:
    - If Year of the onset date is the same as Year of the first administration date, the imputed onset date will be imputed as the minimum of the first administration date/time and the AE end date (imputed if needed).
    - Otherwise, the missing Day & Month will be replaced by “01 JAN.”
  - If a partial AE start date is consistent with the actual start date being on Day 1, and either the AE end date information is completely missing, or the complete or imputed AE end date/time information indicates that the AE did not end before Day 1, the imputed AE start date will be Day 1 in the following scenarios:
    - The AE start time is missing (the AE will be flagged as treatment-emergent following the first dose of study treatment)
    - The AE start time is after the date/time of first dosing of study treatment on Day 1 (the AE will be flagged as treatment-emergent following the first dose of study treatment)
    - The AE start time is before the time of first dosing of study treatment on Day 1, and imputing the AE start date as Day 2 instead of Day 1 would be inconsistent with the partially recorded AE start date (e.g., the calendar month for Day 2 is not the same as for Day 1), or with the complete or imputed AE end date/time (in this case, the AE will not be flagged as treatment-emergent following the first dose of study treatment).
  - Missing start time will be imputed with the time of administration if the day of AE start date and administration are identical, or with 00:00 otherwise.
- Completely missing onset dates for AEs will be imputed by the first administration date and the AE will be considered as treatment-emergent unless the end date/time of the AE (imputed if needed) or the end year of the AE (if day and month are missing) is entered

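### The adverse-event overviews in SAP 5.6 are not limited to treatment-emergent events, and no listed table gives non-ocular or overall TEAE incidence by treatment group

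*SAP*

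**What the plan says.** SAP 5.6 defines a TEAE and then lists the tables. Only two titles carry the treatment-emergent restriction: the ocular table for the treated eye, "Summary of Ocular Treatment-Emergent Adverse Events for Treatment Eye during the overall study period by MedDRA System Organ Class and Preferred Term (Safety Population", and its twin for the contralateral eye. The three overviews do not carry it. They are "Overview of Ocular Adverse Events for Treatment Eye during the overall study period (Safety Population", the matching contralateral-eye table, and "Overview of Non-Ocular Adverse Events during the overall study period (Safety Population". The list ends with bare entries for SAEs and AESIs.

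For both event types the reporting period is given as "and during the overall study period (i.e., up to the last visit for the last subject". That fixes when counting stops but not when it begins.

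The Safety Analysis Set (SAP 4) is "All screened subjects who were randomized and received at least one dose of study treatment". SAP 5.6.1 adds "Imputation of missing/partial AE date/time will be done only to identify TEAEs".

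On the protocol side, section 9.4.1 states that events outside medical history and "occurring before first dose of study treatment will be captured as a non-treatment emergent AE". Section 10.9.1 commits to this output: "The overall incidence of TEAEs will be summarized by treatment group and classified by SOC and PT". It makes no ocular restriction.

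SAP 6 says that, because the study stopped early, there is no formal analysis and the only AE tables are overviews. SAP 8 places the table shells in a separate document.

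**The concern.** After the early stop, these tables are the main tabulated safety result. Two things are at stake.

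- **What the overviews count.** If pre-dose events enter a by-arm table, it mixes events that treatment could have caused with events that it could not. Randomization took place at Day 1 (SAP 3.2), so screening events carry no information about the arms and can only blur a difference between them.
- **What is missing.** A reader of the protocol expects the number of subjects with any TEAE, by group. The listed tables give ocular TEAEs for each eye. For non-ocular events they give only an overview whose scope is not stated. No listed table gives a subject-level TEAE figure across both eyes and non-ocular events.

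**Working it through.** The documents state no AE rate, so there is no plan figure to reproduce. The check compares the texts and then illustrates the size on assumed rates.

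**Step 1. Are pre-dose events in the data and not excluded?** Protocol 9.4.1 records them as AEs flagged non-treatment-emergent. Protocol 5.2 allows up to 12 weeks of screening. The Safety Analysis Set removes subjects who were never dosed, but not the pre-dose events of those who were. Nothing in SAP 5.6 removes such events from the overviews. As written, they are not excluded.

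**Step 2. Is the protocol's TEAE output delivered?**

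| Output | TEAE-limited table listed in SAP 5.6? |
|---|---|
| Ocular, treated eye, by SOC and PT | Yes |
| Ocular, contralateral eye, by SOC and PT | Yes |
| Non-ocular, by SOC and PT | No |
| Any TEAE, each subject counted once, by group | No |

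**Step 3. How much could pre-dose events attenuate a difference?** Let p_A and p_S be the TEAE risks on active and sham, and q the fraction of subjects in every arm with a pre-dose AE, independent of later events. The any-AE risk is 1 − (1 − p)(1 − q), so the difference is

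[1 − (1 − p_A)(1 − q)] − [1 − (1 − p_S)(1 − q)] = (1 − q)(p_A − p_S).

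All rates here are assumptions. For a 20-point true difference (40% versus 20%):

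- q = 5%: 20 × 0.95 = 19 points
- q = 20%: 20 × 0.80 = 16 points
- q = 30%: 20 × 0.70 = 14 points

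One way to give q a scale is to let events occur before dosing at the constant rate seen on sham afterwards. Then q = 1 − (1 − p_S)^(12/weeks of follow-up). With p_S = 0.40 and p_A = 0.65 (difference 0.25):

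- 104 weeks: q = 0.057, difference 0.236
- 52 weeks: q = 0.111, difference 0.222
- 26 weeks: q = 0.210, difference 0.197

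Across sham risks of 0.20 to 0.60 and follow-up of 26 to 104 weeks, q runs from 0.025 to 0.345. This uses the full 12-week screening window and ignores the medical-history rule in Protocol 9.4.1, so it leans high.

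**Step 4. Can the total be read from the split tables?** Not by addition. Take the planned 27 per arm and assumed counts of 12 (treated eye), 4 (contralateral eye) and 12 (non-ocular). The number of subjects with any event lies between max(12, 4, 12) = 12, which is 12/27 = 44%, and min(27, 12 + 4 + 12 = 28) = 27, which is 100%. These counts are illustrative, and actual enrolment is not given.

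**The case against.** The strongest reply is that the scope of the overviews is being inferred from their titles. The shells are not among the documents and may contain TEAE rows. The TEAE flag is derived, and time to onset is measured from the last dose, which has no meaning for a pre-dose event. The section may well have been written with post-dose events in mind. This stands as a reason for caution: what the text shows is an unstated period start, not proof that pre-dose events will be counted.

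Four stronger readings are tempting, and the documents do not support them.

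- **That screening events do dilute the arm differences.** This depends on the shells and on an unknown q. Protocol 9.4.1 sends significant conditions found during screening to medical history, which shrinks the pool of pre-dose AEs. At q = 5% the loss on a 20-point difference is 1 point, or 0.01 × 27 = about 0.3 of a subject in an arm of 27. SAP 6 plans no formal comparison.
- **That the ocular/non-ocular split is a fault.** It matches the protocol's safety endpoint, and only one eye is dosed. What is missing is a combined row.
- **That the total cannot be recovered.** SAP 5.7 plans by-subject listings of ocular and non-ocular AEs, so it can be rebuilt by hand.
- **That serious events by arm are unavailable.** The SAE and AESI entries are bare list items, and their scope and split are not stated.

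The reduced scope is also disclosed in SAP 6. That explains a shorter output list. It does not say that the overall TEAE summary is dropped, and it sits uneasily with SAP 5.6, which still lists TEAE tables by SOC and PT. Protocol 10.9.1 also provides for summaries of all AEs, but in addition to TEAE incidence, not in place of it.

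**Conclusion.** The point holds in a limited form. As listed, the three overviews are not restricted to TEAEs and their period has no stated start. No listed table gives non-ocular TEAE incidence or the subject-level overall TEAE incidence by group that Protocol 10.9.1 plans, and SAP 6 does not name this as a change.

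Any attenuation from pre-dose events is conditional on the shells not separating them. Its size is (1 − q) on the risk difference, assuming the same q in each arm and independence from later events. The documents do not give q. I judge it probably small because of the medical-history rule, though short actual follow-up would raise its relative weight. The missing table does not depend on these assumptions. It affects a descriptive result, and the planned listings offer a laborious way round it.

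**What to change.** - Start the overview period at first dose, or restrict the three overviews and the SAE and AESI summaries to events carrying the existing TEAE flag. Show pre-dose AEs in a separate labelled row or leave them to the listing.
- Add one summary by treatment group that counts each subject once for any TEAE, any serious TEAE and any related TEAE, across both eyes and non-ocular events. Include a sham column: the column order in SAP 5.4 names only the two ultevursen regimens and all subjects.
- State in SAP 6 whether the non-ocular TEAE table by SOC and PT is kept or dropped, so that the section agrees with SAP 5.6 and accounts for Protocol 10.9.1.

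The cost is SAP wording and one short table. The flag is already derived under SAP 5.6.1, so no new data are needed. If the shells already do this, only the wording changes.

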#### **5.6.1. Partial and Missing Date/Time for Adverse Events**

Imputation of missing/partial AE date/time will be done only to identify TEAEs.

AE onset dates

- Partially missing onset date/time will be imputed as follows:
  - When only Day is missing:
    - If Month & Year of the onset date are the same as Month & Year of the first administration date, the imputed onset date will be imputed as the minimum of the first administration date/time and the AE resolution date (imputed if needed).
    - Otherwise, the missing day will be replaced by “1.”
  - When Day & Month are missing:
    - If Year of the onset date is the same as Year of the first administration date, the imputed onset date will be imputed as the minimum of the first administration date/time and the AE end date (imputed if needed).
    - Otherwise, the missing Day & Month will be replaced by “01 JAN.”
  - If a partial AE start date is consistent with the actual start date being on Day 1, and either the AE end date information is completely missing, or the complete or imputed AE end date/time information indicates that the AE did not end before Day 1, the imputed AE start date will be Day 1 in the following scenarios:
    - The AE start time is missing (the AE will be flagged as treatment-emergent following the first dose of study treatment)
    - The AE start time is after the date/time of first dosing of study treatment on Day 1 (the AE will be flagged as treatment-emergent following the first dose of study treatment)
    - The AE start time is before the time of first dosing of study treatment on Day 1, and imputing the AE start date as Day 2 instead of Day 1 would be inconsistent with the partially recorded AE start date (e.g., the calendar month for Day 2 is not the same as for Day 1), or with the complete or imputed AE end date/time (in this case, the AE will not be flagged as treatment-emergent following the first dose of study treatment).
  - Missing start time will be imputed with the time of administration if the day of AE start date and administration are identical, or with 00:00 otherwise.
- Completely missing onset dates for AEs will be imputed by the first administration date and the AE will be considered as treatment-emergent unless the end date/time of the AE (imputed if needed) or the end year of the AE (if day and month are missing) is entered

and is before the first administration date. If the end date/time is before the first administration date, the AE will not be considered as treatment-emergent.

#### AE end dates

- If Day only is missing, incomplete end dates will be replaced by the last day of the month if it is not resulting in a date later than the date of the subject's last visit. In the latter case, the date of the subject's last visit will be used to impute the incomplete end date.
- If Day & Month are missing, Day & Month will be replaced by 31DEC if it is not resulting in a date later than the date of the subject's last visit. In the latter case, the date of the subject's last visit will be used to impute the incomplete end date.
- If the AE end date is completely missing, the AE will be assumed to be ongoing on the date of the subject's last visit and the incomplete end date will not be imputed.

## 5.7. Other Data Listings to be Generated

The following by-subject data listings for the Safety Population will be provided:

- Subject Disposition
- Screen Failures (All Screened Subjects)
- Demographic and Baseline Characteristics (Safety Population)
- Non-Ocular Medical History (Safety Population)
- Ocular Medical History (Safety Population)
- Study Drug Administration of the TE (Safety Population)
- Study Drug Administration of the CE (Safety Population)
- BCVA Based on ETDRS (Safety Population)
- Low Luminance Visual Acuity (LLVA) (Safety Population)
- Spectral Domain Optical Coherence Tomography (SD-OCT) (Safety Population)
- Static Perimetry (Safety Population)
- Microperimetry (Safety Population)
- Full Field Stimulus Threshold (FST; Safety Population)
- Patient Global Impressions of Severity (PGI-S) and Patient Global Impressions of Change (PGI-C) (Safety Population)

- Veterans Affairs Low-Vision Visual Functioning Questionnaire – 20 (Safety Population)
- Ophthalmic exam (Safety Population)
- Non-Ocular Adverse Events (Safety Population)
- Ocular Adverse Events (Safety Population)
- Prior and/or Concomitant Medications (Safety Population)
- Laboratory results: Hematology, Coagulation, and Chemistry (Safety Population)

## **6. CHANGES TO PLANNED ANALYSES**

As the study is prematurely stopped by Sponsor's decision, no formal statistical analysis will be produced. Only disposition, demographic and baseline characteristics, and overview of AEs will be summarized in tables. By-subjects data listings will be produced based on raw data.

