10.6 Subject Disposition, Demographics and Baseline Disease Characteristics

Subject disposition will be summarized for All Screened Subjects population by dose group.

The number and percentage of subjects who receive ultevursen or the sham-procedure will be tabulated by the number of doses and the treatment group.

Subject demographics and baseline characteristics will be summarized for each treatment group and for all subjects combined. Subject characteristics at baseline include age, race, body weight, and height. Baseline disease characteristics include ophthalmic examinations, measurements and tests, as previously described.

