10.8 Efficacy Analyses

The efficacy evaluations will include evaluations of the endpoints listed in Section [4.1](#).

Descriptive statistics of clinical efficacy will be tabulated by dose group, and if appropriate, for dose groups combined.

All continuous endpoints will be summarized using the following descriptive statistics: number of subjects, mean, standard deviation, standard error, median, minimum, maximum and 95% confidence intervals for the mean. Categorical endpoints will be summarized using the following: number of subjects, frequency, percentages and 95% confidence intervals. If data appear highly skewed, natural log or other transformation may be used to compute summary statistics.

Continuous efficacy endpoints will be summarized and may be analyzed using appropriate parametric and/or nonparametric inference tests.

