### **3. STUDY DESIGN**

#### **3.1. Synopsis of Study Design**

PQ-421a-003 is a double-masked, randomized, controlled, multiple-dose study to evaluate the efficacy, safety and tolerability of ultevursen in subjects with RP due to mutations in exon 13 of the *USH2A* gene.

At study start, subjects are randomized to one of the following treatment groups:

- Group 1: Ultевурсен 180/60 μg (180 μg loading dose administered on Day 1, 60 μg maintenance dose administered at Month 3, and every 6 months thereafter; n = 27)
- Group 2: Ultевурсен 60/60 μg (60 μg loading dose administered on Day 1, 60 μg maintenance dose administered at Month 3, and every 6 months thereafter; n = 27)
- Group 3: Sham-procedure (administered on Day 1, Month 3, and every 6 months thereafter; n = 27)

Please refer to Section 4.2 of the study protocol for details regarding the study design.

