### **5.4. General Statistical Methods**

All output will be incorporated into Rich Text Format (RTF) files and bookmarked PDFs, sorted and labeled according to the International Conference on Harmonisation (ICH) recommendations, and formatted to the appropriate page size(s).

Tabulations will be produced for appropriate disposition and demographic characteristics.

For measurements of continuous variables, summary statistics of absolute values will be reported and will include n, mean, standard deviation, median, and minimum and maximum values. The number of missing values will be displayed in parenthesis next to 'n'. Mean, standard deviation, median, will be presented with one more decimal place compared to the raw data, and minimum and maximum will be presented with the same number of decimal places as the raw data.

For categorical variables, summary tabulations of the number and percentage within each category of the parameter will be presented (as well as the number for missing data).

Denominator for percentages is column N. Percentages will be rounded to one decimal place.

Therefore, there may be cases where for instance the total of the percentages does not exactly equal 100%.

Where appropriate, data will be listed by eye (i.e., TE, CE).

In summary tables the study treatments will be presented in the following order: 'Ultevursen 180/60 µg', 'Ultevursen 60/60 µg', and 'All Subjects'.

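### The SAP 5.4 column order for summary tables omits the sham arm and contradicts the rest of the SAP; separately, descriptive efficacy tables could be restored cheaply

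*SAP*

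**What the plan says.** **Table columns.** SAP 5.4 states: "In summary tables the study treatments will be presented in the following order". It then names ultevursen 180/60 µg, ultevursen 60/60 µg and All Subjects. Sham is not named. SAP 3.1 lists it as one of the three randomized arms: "Group 3: Sham-procedure (administered on Day 1, Month 3, and every 6 months thereafter; n = 27". SAP 3.2 gives 1:1:1 allocation to the same three arms. SAP 5.5.1 (disposition), 5.5.2 (baseline) and 5.6 (adverse events) each ask for summaries by treatment group, and the treatment-emergent definition in 5.6 counts the sham procedure as study drug. The protocol agrees. Section 10.6 says "Subject demographics and baseline characteristics will be summarized for each treatment group and for all subjects combined", and section 10.9.1 says "The overall incidence of TEAEs will be summarized by treatment group and classified by SOC and PT".

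**Efficacy summaries.** Protocol 10.8 says "Descriptive statistics of clinical efficacy will be tabulated by dose group, and if appropriate, for dose groups combined". For continuous endpoints it specifies "number of subjects, mean, standard deviation, standard error, median, minimum, maximum and 95% confidence intervals for the mean". SAP 6 attributes the reduced plan to the sponsor's early stop, rules out formal analysis, and then limits the tables: "Only disposition, demographic and baseline characteristics, and overview of AEs will be summarized in tables". Efficacy and patient-reported data go to by-subject listings (SAP 5.7). SAP 5.2 defines baseline BCVA. For continuous variables, SAP 5.4 provides only that "summary statistics of absolute values will be reported".

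**The concern.** The trial was set up to compare each ultevursen regimen with sham; the primary endpoint in Protocol 4.1.1 is worded that way. After early termination, the few remaining tables are the main place where the arms can be seen side by side, and SAP 2.2 makes these outputs the basis of the abbreviated study report. If the programmer follows the SAP 5.4 order as written, adverse event rates on active treatment appear with no control column beside them. Baseline comparability with sham cannot be read off the tables either.

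The efficacy point is weaker but related. With listings only, each reader who wants BCVA change by arm must derive it and choose visits and subsets alone. A short set of tables fixed in the SAP would give everyone the same summary.

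**Working it through.** **1. Arms against columns.** The planned total reproduces: 3 × 27 = 81, as in the protocol synopsis.

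| Arm (SAP 3.1) | Planned n | Named in the SAP 5.4 column order? |
|---|---|---|
| Ultevursen 180/60 µg | 27 | Yes |
| Ultevursen 60/60 µg | 27 | Yes |
| Sham procedure | 27 | No |

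Planned subjects without a column of their own: 27/81 = 33.3%.

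**2. Which tables are affected.** The 5.4 sentence applies to summary tables in general, so it covers the disposition, baseline and adverse event tables that SAP 6 keeps. The sections defining those tables (5.5.1, 5.5.2, 5.6) say by treatment group, which under SAP 3.1 and 3.2 means three groups. Both instructions cannot be followed. The 5.4 sentence reads as complete, with no sign that a third arm was blacked out.

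**3. What could be recovered about sham if 5.4 were followed.**
- *All Subjects pools three arms.* A sham count is the total minus the two ultevursen counts. A sham mean follows, up to rounding, from (N × overall mean − n₁ × mean₁ − n₂ × mean₂)/(N − n₁ − n₂). Sham medians and ranges cannot in general be obtained this way.
- *All Subjects pools ultevursen only.* Subtraction gives nothing. The SAP does not define the column, but Protocol 10.6, quoted above, points to the three-arm reading.
- *Either way.* The SAP 5.7 listings cover the Safety Population, which includes dosed sham subjects. Sham results can be rebuilt by hand from them, provided the listings (drug administration, for instance) identify the arm.

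**4. Efficacy measures against outputs.** Protocol 4.1.1 and 4.1.2 name 8 efficacy and patient-reported measures: BCVA, ellipsoid zone on SD-OCT, LLVA, microperimetry, FST, VA LV VFQ-20, PGI-S and PGI-C. SAP 5.7 covers all 8, in 7 listings (PGI-S and PGI-C share one). Post-baseline tables allowed by SAP 6: 0. The only tabulated efficacy variable is baseline BCVA (SAP 5.5.2).

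**5. How precise restored tables might be.** The documents give neither the number randomized, nor the number reaching each visit, nor an SD. Only n = 27 comes from the plan; 15, 10 and 5 are assumptions.
- Half-width of the 95% CI for an arm mean, in SD units: t(0.975, n−1)/√n.
- Upper exact two-sided 95% limit when 0 of n lose 15 or more letters: 1 − 0.025^(1/n).

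| n per arm | Half-width (SD) | Upper limit for 0 of n |
|---|---|---|
| 27 (planned) | 2.056/5.196 = 0.396 | 12.8% |
| 15 (assumed) | 2.145/3.873 = 0.554 | 21.8% |
| 10 (assumed) | 2.262/3.162 = 0.715 | 30.8% |
| 5 (assumed) | 2.776/2.236 = 1.242 | 52.2% |

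**The case against.** **On the sham column.** Three operative sections imply a sham column, against one formatting sentence that leaves it out. The table shells are in a separate document (SAP 8) that is not available here and may already be right. This stands: the point is an internal contradiction, probably a drafting slip, and the documents do not show that the sponsor means to hide the control arm. A reader might also infer that nothing about sham could be recovered. That goes too far, because the Safety Population listings remain.

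**On the efficacy tables.** The change is declared in the section meant for changes, in a plan that calls itself abbreviated, and Protocol 10.1 leaves methodology to the SAP. SAP 2.2 appears to begin after removed text, so a fuller reason may exist. Protocol 10.8 speaks of dose groups and does not say whether sham is one. All of this stands, so it would be wrong to call the listings-only choice a hidden or clear breach of the protocol. What remains is that the visible reason does not explain omitting simple summaries of data already being listed.

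**Other readings to avoid.** One might say that change from baseline is specified nowhere. Protocol 4.1.1 names it for BCVA; the SAP simply has no table that uses it. One might also call the absence of syndromic status, the stratification factor, from the baseline table an error. Protocol 10.6 does not list it among the baseline characteristics, so adding it is a preference.

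**Conclusion.** The main point holds as an inconsistency in the SAP. The SAP 5.4 column order omits one of three randomized arms (27 of 81 planned subjects, 33.3%) and conflicts with SAP 3.1, 3.2, 5.5.1, 5.5.2 and 5.6. If 5.4 governs, the retained tables lose their comparator column and sham results must be reconstructed. If the by-treatment-group sections or the unseen shells govern, the tables are sound and only the sentence is wrong. Either way it should be corrected.

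The secondary point is an improvement, not an error: none of the 8 efficacy and patient-reported measures has a post-baseline table, although Protocol 10.8 planned descriptive tabulation. The benefit depends on how many subjects were followed, which the documents do not say. The precision figures for fewer than 27 per arm rest on assumed numbers.

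A separate matter needs reconciling: SAP 5.5.1, 5.6 and 5.7 provide for study treatment in the contralateral eye, whereas Protocol 4.2 says that eye is not dosed.

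**What to change.** 1. **SAP 5.4:** add the sham procedure to the column order and state that the all-subjects column pools all three arms, in line with Protocol 10.6. Check the shells against this. Cost: one column label and one definition.

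2. **SAP 6 and 5.4 (improvement):** add descriptive tables by randomized arm on the existing Safety Analysis Set, without p-values. At a minimum, give treated-eye BCVA, observed and as change from the SAP 5.2 baseline, at each scheduled visit (n, mean, SD, median, range, 95% CI), and the number losing 15 or more letters. Label them descriptive because of early termination, and say so if they were specified after unmasking. Cost: a few tables from data already being listed, with no new analysis population. The downside is that the estimates may be imprecise, since the actual numbers are not given.

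3. If the sponsor keeps listings only, SAP 6 should say why simple summaries are omitted. Cost: one sentence.
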